- a) Primary Outcome
 - a) Outcome Measure Title: Reduction in severity of CINV
 - b) Outcome Measure Description: Assessed by the mean score of the Antiemesis (MAT) tool, which measures acute and delayed CINV across patients' chemotherapy regimens.
 - c) **Outcome Measure Timeframe**: Data tool collected during study visits 1, 2, 3, and 4.
- b) Secondary Outcome
 - a) Outcome Measure Title: Reduction in Antiemetic Use
 - b) **Outcome Measure Description**: Assessed by the mean score of antiemetics diary, which measures the usage frequency (date and time) and type (name) of antiemetic medications.
 - c) **Outcome Measure Timeframe**: Data diary collected during study visits 1, 2, 3, and 4.
- c) Exploratory Outcome
 - a) Outcome Measure Title: Improved Resilience
 - b) **Outcome Measure Description**: Assessed by the mean score of the Connor-Davidson Resilience Scale (CD-RISC), which measures the participants' resilience pre and post the intervention.
 - c) Outcome Measure Timeframe: Data collected at baseline and final visit.
- d) Exploratory Outcome
 - a) Outcome Measure Title: Reduction in Psychological Distress Symptoms
 - b) **Outcome Measure Description**: Assessed by the mean score of the psychological distress symptoms visual analog scale the patients' anxiety, stress, and depression at pre-and post-assessment.
 - c) Outcome Measure Timeframe: Data collected at baseline and final visit.
- e) Exploratory Outcome
 - a) Outcome Measure Title: Improved Quality of Life
 - b) **Outcome Measure Description**: Assessed by the mean score of Functional Assessment of Chronic Illness Therapy General (FACIT-G), which measures the

patients' quality of life and well-being at pre-and post-assessment.

c) Outcome Measure Timeframe: Data collected at baseline and final visit.

The study objectives and endpoints were selected because (a) more research is necessary to understand the effects of aromatherapy on moderate and high emetogenic chemotherapy regimens in an outpatient setting; (b) the literature suggests that CINV has a relationship with decreased quality of life and increased antiemetic usage and psychological distress symptoms; (c) the relationship between CINV and resilience has not been established. However, literature has shown a relationship between resilience and a reduction in psychological distress symptoms and improved quality of life.

9) Procedures Involved*

The study will continue as follows:

Initial visit

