All endpoints will be evaluated using parametric analysis to examine the difference between the two conditions across the 3-time points for primary endpoints (CINV and Use of Antiemetics) and 2-time points for secondary endpoints (resilience, psychological distress, and quality of life). The analysis will be conducted using SPSS Version 26. For binary outcomes (CINV), logistic regression will be used. For continuous outcomes (antiemetic use, resilience, psychological distress, and quality of life) a Mixed ANOVA will be used with condition as the between-subjects variable and change over time on the outcome as the within-subjects variable. Sphericity and homogeneity of variance assumptions will be tested prior to interpretation of the results, and the

Greenhouse-Geisser correction will be implemented if Sphericity is violated. A type I error rate of .05 will be used to determine significance for all analyses.

Outcome	Measure	Type of measurement
CINV	MAT	Binary
Use of antiemetics	Antiemetic Diary	Continuous
Resilience	CD-RISC	Continuous
Psychological Distress	Visual Analog Scale	Continuous
Quality of Life	FACIT-G	Continuous

2. Analysis of the Primary Endpoint(s)

For CINV, logistic regression will be used to determine whether the use of aromatherapy decreases the risk for any of the following outcomes: acute nausea, delayed nausea, acute vomiting, or delated vomiting. For use of antiemetic medication, a Mixed ANOVA will be used to evaluate differences between conditions (aromatherapy group vs. treatment as usual) across the 3-time points (Visit 1, Visit 2, and Visit 3). Time x treatment effects will be evaluated as well as main effects.

3. Analysis of the Secondary Endpoint(s)

For resilience, psychological distress, and quality of life, a Mixed ANOVA will be used to evaluate differences between conditions (aromatherapy group vs. treatment as usual) across the 2-time points (Initial visit and final visit). Time x treatment effects will be evaluated as well as main effects

4. Baseline Descriptive Statistics

Participant demographic characteristics will be analyzed using descriptive statistics. Specifically, frequencies and percentages will be reported for categorical variables, and means and standard deviations will be reported for continuous variables.

12) **Provisions to Monitor the Data to Ensure the Safety of Subjects***

This section is not applicable. The risks of this study are minimal.

13) Withdrawal of Subjects*

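### The plan does not say how a participant's repeated binary CINV records enter the logistic model, or at which visit (or averaged over which visits) the arms are compared

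*Combined protocol and SAP*

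**What the plan says.** Section 11, General Approach, states that the analysis is meant "to examine the difference between the two conditions across the 3-time points for primary endpoints (CINV and Use of Antiemetics"). It classes CINV, measured by the MAT tool, as binary and says "For binary outcomes (CINV), logistic regression will be used". Antiemetic use, resilience, distress and quality of life get a Mixed ANOVA with "change over time on the outcome as the within-subjects variable", plus a sphericity check and correction. The significance level is set once: "A type I error rate of .05 will be used to determine significance for all analyses".

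The next subsection, on the primary endpoints, reads "For CINV, logistic regression will be used to determine whether the use of aromatherapy decreases the risk for any of the following outcomes", and lists acute nausea, delayed nausea, acute vomiting and delayed vomiting. That sentence names no visit. The one after it, on antiemetic use, names Visits 1, 2 and 3. The paragraph then closes with "Time x treatment effects will be evaluated as well as main effects".

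Section 9 (Procedures Involved) and Table 2 have a completed MAT form collected at Visits 1, 2 and 3 and none at the initial visit. The Study Endpoints section describes the primary outcome differently: "Assessed by the mean score of the Antiemesis (MAT) tool", with the timeframe "Data tool collected during study visits 1, 2, 3, and 4".

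**The concern.** Three MAT forms from one person are not three independent observations. Someone who is nauseated after one cycle is more likely to be nauseated after the next. Logistic regression without a participant term or a clustered variance treats every row as independent, so with stacked rows the interval for the arm effect is too narrow whenever the within-participant correlation is positive.

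The plan provides for repeated measures in every continuous outcome but not in its primary one. At least three analyses fit the text: stacked rows, one model per visit, or one value per participant. They differ in error rate and power, and nothing fixes the choice before the data are seen.

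**Working it through.** The plan gives no power calculation, ICC or expected rates for CINV, so there is no figure of its own to reproduce. The check asks what each reading implies.

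**Inputs from the documents**
- Records per participant: m = 3 (Table 2; three time points in the General Approach).
- Total sample: 100 (section 6).
- Significance level: .05, sidedness not stated.
- Background rates, used only for illustration: 40% for CINV, and 71% for nausea in breast cancer.

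**Assumptions**
- ICC of 0.1, 0.3, 0.5 or 0.7, equal between any two cycles.
- 50 per arm (the allocation ratio is not stated).
- Complete data and a two-sided test.
- A third occurrence rate of 20%.

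**Reading 1: stacked rows, arm effect tested**

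The design effect is DE = 1 + (m - 1) × ICC = 1 + 2 × ICC. The actual two-sided error is 2 × [1 - Φ(1.960/√DE)].

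| ICC | DE | √DE | 1.960/√DE | Two-sided error |
|---|---|---|---|---|
| 0.1 | 1.2 | 1.095 | 1.789 | 0.074 |
| 0.3 | 1.6 | 1.265 | 1.549 | 0.121 |
| 0.5 | 2.0 | 1.414 | 1.386 | 0.166 |
| 0.7 | 2.4 | 1.549 | 1.265 | 0.206 |

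A beta-binomial simulation with no arm effect (40,000 replicates; occurrence 20%, 40% and 71%) agrees: 7.0-7.7%, 11.9-12.5%, 16.6-16.9% and 20.5-21.0%. At ICC 0 a run at 40% and 71% gave 5.2% and 4.9%, so the set-up is sound.

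If the .05 were one-sided, 1 - Φ(1.645/√DE) gives 6.7%, 9.7%, 12.2% and 14.4%.

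**The term tested matters.** With arm-by-visit terms added to the stacked model:
- the arm effect averaged over visits is still inflated (6.6-7.5%, 11.4-12.1%, 15.9-16.4%, 19.8-20.4%);
- the arm coefficient at the reference visit is not (4.1-5.2%);
- the interaction test is too conservative (2.7-3.3% at ICC 0.1, falling to about 0% at 0.7).

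**Reading 2: one model per visit**

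Each test holds about 4-5%. If no visit is named, the chance that at least one of three falls below .05 would be 1 - 0.95³ = 14.3% under independence. In the simulations it was 9-15%.

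**Reading 3: one value per participant**

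If prespecified, this has neither problem. The plan names no such value.

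**Effect of the choice on power**

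Take 40% against an assumed 20%, with 50 per arm. A single named visit has 59% power. The average over three visits, with effective records per arm of 150/DE, has 85%, 77% and 69% at ICC 0.3, 0.5 and 0.7. Treating 150 records per arm as independent would show an apparent 97%.

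**Check of the remedy**

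A participant-clustered robust test gave 4.3-5.0% with a small-sample correction and 4.8-5.5% without. A GEE with arm and cycle terms, fitted directly at 40% and 71% occurrence (600 replicates, Monte Carlo standard error about 0.9 percentage points), gave 4.0-6.3%. Ordinary logistic regression on the same data gave 6.2-23.5%.

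**The case against.** The strongest reply is that the plan names logistic regression without qualification, which does not rule out a GEE or mixed form. It also never says that rows will be stacked. The CINV sentence omits the time points and speaks of risk, which fits one value per participant as well. The closing sentence on time-by-treatment and main effects could be read to cover CINV too. The arms and the direction of benefit are clear.

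Most of this stands, and it limits the point. A reader might infer that the plan prescribes an analysis assuming independence, and hence that the primary test is inflated. The documents do not support that: stacking is one reading among several, and the 7% to 21% range applies only under it and at ICCs that are assumed. A reader might also infer that no comparison is defined at all; in fact only the visit or averaging rule is missing.

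The reply does not close the gap. Applying the closing sentence to CINV would still leave the within-participant correlation and the primary contrast undefined. The mean score in Study Endpoints could suggest a per-participant summary, but the analysis section types CINV as binary and no rule turns the score into one binary value.

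**Conclusion.** The point holds as an omission in the primary analysis with a measurable risk, not as a demonstrated error. It should be fixed before analysis. That the handling of repeated records and the visit or average to be tested are unspecified is certain from the text supplied. The size depends on the reading:
- stacked rows with the arm effect tested: about 7% to 21% two-sided error for ICC 0.1 to 0.7;
- separate visits with none named: about 9-15% chance of at least one false positive per CINV outcome;
- one prespecified value per participant: no excess.

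These are sensitivity ranges under equal correlation and complete data (the simulations also assume 50 per arm), not estimates for this trial.

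**What to change.** For each binary CINV outcome, specify a logistic model that accounts for repeated records within participant, with arm and cycle as terms. Either a GEE with exchangeable working correlation and robust standard errors, or a mixed logistic model, will do. Name one of them, since their odds ratios have different meanings (population-averaged versus participant-specific). Withdrawal for essential-oil sensitivity arises from inhaler use, so missing records may differ by arm. An unweighted GEE needs stronger missing-data assumptions than a likelihood-based mixed model, which is relevant to the choice. Prespecify the two-sided arm effect at .05, averaged over the three cycles, as the single test for that outcome.

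A small-sample correction is optional at this size. If one is wanted and SPSS Version 26 does not offer it, name a second package.

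The cost is SAP wording, with no new data or visits. Intervals will be about 1.10, 1.26, 1.41 or 1.55 times (√DE) as wide as under unadjusted stacking at ICC 0.1, 0.3, 0.5 or 0.7, which reflects the true uncertainty.

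Two separate points remain. One test per outcome still leaves four tests at .05 (1 - 0.95⁴ = 18.5% if independent). The mean score and four visits in Study Endpoints also still have to be reconciled with the binary outcome and three collections elsewhere.

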A study team member and participant will meet during the participant's scheduled CTU appointment to collect their MAT tool and antiemetic/aromatherapy diary. During this interaction, the study team member will reinforce instructions and answer any participant's questions, concerns, or confusion regarding the aromatherapy inhaler, MAT tool, and antiemetic/aromatherapy diary. A new study packet and an aromatherapy inhaler, if necessary, will be provided to the participants.

Visit 3: Participants' visit three will take part on their next scheduled chemotherapy infusion – i.e., the participants' third chemotherapy cycle during their study period. A study team member

will give the participant access to complete the following assessments via iPad or laptop: postassessment and demographic form, psychological distress VAS, resilience scale, and FACIT-G.

Arm 1 - Control group:

A study team member and participant will meet during the participants' scheduled CTU appointment to collect their final MAT tool and antiemetic diary. During this interaction, the study team member will assess the participant's study experience and provide the participant with a thank you card appreciation for their study participation.

Arm 2 - Interventional group:

A study team member and participant will meet during the participants' scheduled CTU appointment to collect their final MAT tool and antiemetic/aromatherapy diary. During this interaction, the study team member will assess the participant's study experience and provide the participant with a thank you card appreciation for their study participation.

If a participant is admitted to an SCCC's inpatient unit or has their chemotherapy temporally held during their study period, the study procedures will be postponed until their next regularly scheduled outpatient CTU visit. Participants' known admissions will be noted in the respective participant's study notes.

Table 2

Timepoints	1	2	3	4
Visits	Initial	1	2	3 (Final)
Assessments collected on:				
Demographic	X*			
Pre-assessment	X*			
Psychological distress symptoms (VAS)	X*			X*
Resilience	X*			X*
FACIT-G	X*			X*
MAT tool		Х	Х	Х
Antiemetic diary		Х	Х	Х
Antiemetic/Aromatherapy diary (intervention group only)		Х	Х	Х
Post-assessment				X*

Participant's Study Period and Associated Assessments

Note: (*) indicates measures where data are entered directly in REDCap.

Interventions and Assessment Instruments:

Pre-Assessment and Demographic Checklist:

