Additionally, there is a space to name other complementary methods used to relieve CINV and describe how the CINV was controlled in the antiemetic/aromatherapy diary.

MAT Tool:

The Antiemesis (MAT) tool created by the Multinational Association of Supportive Care in Cancer (Dranisaris et al., 2017) is a user-friendly and reliable tool designed to measure acute and delayed CINV across patients entire chemotherapy regimen. The MAT tool is available in English and Spanish languages. The MAT tool consists of eight items that assess participants' CINV (i.e., occurrence, duration, and frequency). Four items assess the participants' acute phase (i.e., first 24 hours after receiving chemotherapy), and the last four items assess the delayed phase (i.e., day 2 to day 4 after chemotherapy treatment). The MAT tool has been used as a communication tool to facilitate discussions about their CINV to their healthcare providers (Alafafsheh & Ahmad, 2016; Molassiotis et al., 2007; Yamaguchi et al., 2009). This MAT tool has shown good reliability and validity, with Cronbach alpha of 0.77-0.97 in 1200 patients with cancer (Alafafsheh & Ahmad, 2016; Dranisaris et al., 2017; Molassiotis et al., 2007; Yamaguchi et al., 2009).

Antiemetic Diary (Arm 1 - Control Only):

The antiemetic diary allows the participants to record their usage (date and time) and type (name) of antiemetic medications. Additionally, there is a space to name other

complementary methods used to relieve CINV and describe how the CINV was controlled in the antiemetic diary.

Resilience Scale:

The Connor-Davidson Resilience Scale (CD-RISC) will assess the participants' resilience pre and post the intervention (Burns & Anstey, 2010). For this study, we will use the 10-item questionnaire that includes questions such as: are you 'able to adapt to change,' 'can (you) deal with whatever comes,' to 'can handle unpleasant feelings.' This scale has shown good reliability and validity, with Cronbach alpha of 0.88 in 343 patients with cancer and 122 breast patients with cancer (Matzka, Mayer, Köck-Hódi, Moses-Passini, Dubey, Jahn, ... & Eicher, 2016; Scali, Gandubert, Ritchie, Soulier, Ancelin, Chaudieu, & Uddin, 2012).

Psychological Distress Symptoms:

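### The primary endpoint is defined in conflicting ways, and every primary test is run at .05 with no multiplicity rule

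*Combined protocol and SAP*

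**What the plan says.** **Rank of antiemetic use.** Study Endpoints has one primary outcome, CINV severity, and places "Outcome Measure Title: Reduction in Antiemetic Use" under the secondary outcome. The primary objective in section 3 names CINV and antiemetic use together. Section 11, General Approach, speaks of differences "across the 3-time points for primary endpoints (CINV and Use of Antiemetics)".

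**CINV measure.** Study Endpoints: "Assessed by the mean score of the Antiemesis (MAT) tool". Section 11: "For binary outcomes (CINV), logistic regression will be used". The outcome table there has a single CINV row, typed as binary. The MAT description in section 9 reads: "The MAT tool consists of eight items that assess participants' CINV (i.e., occurrence, duration, and frequency)". No scoring rule for a mean is given.

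**Number of tests.** Section 11, Analysis of the Primary Endpoint(s), asks whether aromatherapy lowers the risk of any of four events: nausea and vomiting, each in the acute and the delayed phase. For antiemetic use it calls for the treatment-by-time interaction as well as the main effects, and does not say which is primary.

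**Visits.** Study Endpoints: "Data tool collected during study visits 1, 2, 3, and 4". Section 9 has the study team meet participants at Visit 3 "to collect their final MAT tool and antiemetic diary", and Table 2 marks MAT collection at Visits 1, 2 and 3 only.

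**Error rate.** "A type I error rate of .05 will be used to determine significance for all analyses". The text gives no adjustment, no order of testing, and no statement of whether one or all primary results must be significant.

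**The concern.** The primary endpoint in Study Endpoints, a mean severity score, has no analysis in section 11. The endpoint that section 11 does analyse, binary occurrence, is not the one in Study Endpoints. Success could be claimed on the mean score, a composite, any one of four binary outcomes, the antiemetic main effect or the antiemetic interaction, and each claim could cite the plan.

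This matters more because participants know their arm (inhaler or usual care) and report the outcomes themselves. Nothing written down prevents the endpoint from being chosen after the data are seen. Even with correctly calibrated tests, running several primary tests at .05 each takes the chance of at least one false positive well above .05.

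A second gap sits beside this one. CINV is compared over three visits, but only the continuous outcomes are given a within-patient model. How repeated visits enter the logistic regression is not stated.

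**Working it through.** **Inputs from the documents.** A threshold of .05 per analysis (section 11, General Approach); four CINV events plus antiemetic use (section 11, Analysis of the Primary Endpoint(s)); total sample 100 (section 6). The plan gives no familywise error or power figure to reproduce. A single test at .05 has error 1 − (1 − .05) = .05.

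**Assumptions.** Two-sided tests (sidedness is not stated); equal correlation r between normal test statistics (no correlations are given, so a range is shown); one treatment test for antiemetic use unless stated.

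**Independent tests.** The chance of at least one false positive is 1 − .95^k:
- k = 2 (composite CINV, antiemetic use): 1 − .9025 = 9.75%.
- k = 5 (four CINV outcomes, antiemetic use): 1 − .7738 = 22.6%.

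**Correlated tests.** P(any |z| > 1.96), by one-factor numerical integration:

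| r | k = 2 | k = 5 |
|---|---|---|
| 0 | 9.75% | 22.6% |
| 0.3 | 9.5% | 20.9% |
| 0.5 | 9.1% | 18.3% |
| 0.7 | 8.4% | 14.8% |
| 0.8 | 7.8% | 12.7% |
| 0.9 | 7.0% | 10.2% |

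For r from 0.7 to 0 this is about 1.7–1.95 times .05 for two tests and 3.0–4.5 times .05 for five.

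**Counting the antiemetic interaction too.** With p from the table and the interaction taken as independent of the other tests, the error is 1 − (1 − p) × .95:
- Composite reading: 1 − .9025 × .95 = 14.3% at r = 0; 1 − .9165 × .95 = 12.9% at r = 0.7.
- Four-outcome reading: 1 − .7738 × .95 = 26.5% at r = 0; 1 − .8516 × .95 = 19.1% at r = 0.7.

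**False claims of benefit.** The hypotheses are directional. For r from 0.7 to 0, P(any z < −1.96) is 4.2–4.9% for two tests and 7.4–11.9% for five, against 2.5% for one two-sided test at .05.

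**Illustration of the repeated-visit gap.** The plan does not say how visits enter the model, so this is illustration only. Null simulations assumed 50 per arm, three visits, event rates of 60/60/30/30%, and latent correlations of 0.3–0.7 between visits and between outcomes (nine scenarios of 20,000 trials). Stacking visits as independent rows gave 9.0–16.9% error per CINV test. GEE with robust standard errors gave 4.6–5.4%.

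**The case against.** The error figures depend on which text prevails. If Study Endpoints governs and its single mean-score outcome is tested once, the error is 5%. If every primary result had to be significant before success was claimed, that claim would not be inflated. Section 3 also gives CINV and antiemetic use separate aims and hypotheses, so .05 per hypothesis could be defended if success were defined that way. These points stand as conditions: reconciling the endpoint comes first, and adjustment is needed only if more than one primary test remains. They do not rescue the current text. It contains no such success rule, and Study Endpoints cannot simply govern when its endpoint has no analysis in section 11.

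Three smaller points are fair:
- The four visits in Study Endpoints may be Table 2's timepoint numbering, where timepoint 1 is the initial visit. That suggests a labelling slip, but no MAT is collected at timepoint 1, so the mismatch remains.
- Section 11 leaves the handling of repeated visits in the logistic regression unspecified; it does not prescribe a wrong method.
- The 2.5% comparison needs two-sided testing. With one-sided tests at .05 the benchmark would be 5%, and the independent-test figures would still be 9.75% and 22.6%.

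The lower ends of the ranges rest on assumed correlations. Even at 0.9, though, both readings exceed .05.

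**Conclusion.** The concern holds and must be fixed. The plan contradicts itself on the rank of antiemetic use, the CINV measure and the MAT visits, and leaves open whether CINV is one test or four. With section 11 applied as written, at least one false-positive primary result has probability 8.4–9.75% (composite) or 14.8–22.6% (four CINV tests), and more if the antiemetic interaction also counts. These figures assume calibrated two-sided tests, equal correlations of 0.7 to 0 and one antiemetic test. The contradictions themselves need no assumption.

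**What to change.** Amend the plan before any between-arm comparison:

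1. Reconcile section 3, Study Endpoints and section 11 to one defined primary CINV endpoint and one rank for antiemetic use. The CINV endpoint may be the mean MAT score, with its scoring stated, or one binary outcome. If it is a composite, define it.
2. Reconcile the MAT visits between Study Endpoints and Table 2.
3. Estimate one treatment effect over those visits with a model that accounts for repeated visits per patient: GEE or mixed-effects logistic regression if binary, a repeated-measures model if a score.
4. If antiemetic use stays primary, name one treatment effect as its primary test.
5. If more than one primary test remains, control familywise error at .05 over the whole primary family, antiemetic use included, by Holm or a prespecified fixed sequence. Report all other p-values as nominal.

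**Check of the remedy.** In the same illustrative simulations with GEE, the five-test family has error 16.8–21.5% unadjusted and 3.9–4.8% with Holm. The composite plus antiemetic use has 8.4–9.8% unadjusted and 4.3–5.0% with Holm.

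**Cost.** An amendment and analysis wording, with no new data. Holm's first threshold is .05/2 = .025 or .05/5 = .01. A test with 80% power at .05 then has, at that step, Φ(1.960 + 0.842 − 2.241) = 71% or Φ(1.960 + 0.842 − 2.576) = 59% (normal approximation). A fixed sequence keeps .05 for the first-ranked test, but later tests count only if the earlier ones succeed.

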-

Effects of Aromatherapy on Chemotherapy-Induced Nausea and Vomiting: A Control Trial

IBIS Protocol#: 20201412

Principal Investigator	[name]., RN, MSN, LHRM, CPHQ, CCM	
	School of Nursing and Health Studies	
	University of Miami	
	[name]	
	[contact]	
	[contact]	
Funding Agency		
Version	2.0	
Version Date	09/08/2023	
NCT Number	NCT05319860	

1) **Protocol Title**

Effects of Aromatherapy on Chemotherapy-Induced Nausea and Vomiting: A Control Trial

2) IRB Review History*

Not applicable

3) Objectives*

Primary:

To investigate the effect of aromatherapy inhalation on chemotherapyinduced nausea and vomiting (CINV) and the use of antiemetics among patients with cancer receiving moderate to high emetogenic outpatient chemotherapy regimens.

Secondary:

To investigate the effect of aromatherapy inhalation on resilience, psychological distress symptoms (e.g., stress, anxiety, and depression), and quality of life among patients with cancer receiving moderate to high emetogenic chemotherapy regimens outpatient.

Aims & Hypotheses:

- (1) To investigate the effect of aromatherapy inhalation on CINV among patients with cancer receiving moderate to high emetogenic chemotherapy regimens outpatient.
 - (a) Outpatient patients with cancer using aromatherapy inhalation will reduce the discomfort associated with their CINV while receiving moderate to high emetogenic chemotherapy.
- (2) To investigate the effect of aromatherapy inhalation on the use of antiemetics among patients with cancer receiving moderate to high emetogenic chemotherapy regimens outpatient.
 - (a) Outpatient patients with cancer using aromatherapy inhalation will reduce the use of antiemetics while receiving moderate to high emetogenic chemotherapy.
- (3) To investigate the effect of aromatherapy inhalation on resilience among patients with cancer receiving moderate to high emetogenic chemotherapy regimens outpatient.
 - (a) Outpatient patients with cancer using aromatherapy inhalation will have higher levels of resilience while receiving moderate to high emetogenic chemotherapy.
- (4) To investigate the effect of aromatherapy inhalation on psychological distress symptoms of stress, anxiety, and depression among patients with cancer receiving moderate to high emetogenic chemotherapy regimens outpatient.

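### The primary outcome is severity of CINV by mean MAT score, but the analysis plan tests only whether nausea or vomiting occurred, so the stated primary outcome has no between-arm test

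*Combined protocol and SAP*

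**What the plan says.** All places are in the combined protocol and SAP.

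- **Study Endpoints, Primary Outcome.** The title is "Outcome Measure Title: Reduction in severity of CINV", and the description is "Assessed by the mean score of the Antiemesis (MAT) tool".
- **Section 3, Objectives.** Hypothesis 1(a) is that "Outpatient patients with cancer using aromatherapy inhalation will reduce the discomfort associated with their CINV". The primary objective and Aim 1 speak only of an effect on CINV, which fits either severity or occurrence.
- **Section 11, 1. General Approach.** The opening sentence promises parametric analysis of all endpoints "across the 3-time points for primary endpoints (CINV and Use of Antiemetics" being the two named). It then assigns logistic regression to binary outcomes, with CINV as the one listed, and adds: "For continuous outcomes (antiemetic use, resilience, psychological distress, and quality of life) a Mixed ANOVA will be used". The outcome table types CINV, measured by MAT, as binary.
- **Section 11, 2. Analysis of the Primary Endpoint(s).** The sentence on this outcome reads: "For CINV, logistic regression will be used to determine whether the use of aromatherapy decreases the risk for any of the following outcomes". The four outcomes listed are acute nausea, delayed nausea, acute vomiting and delayed vomiting.
- **Section 9, MAT Tool.** There are eight items, four acute and four delayed, covering occurrence, duration and frequency. No scoring rule is given and no intensity item is listed.

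Two linked differences concern the same endpoints.

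- **Rank of antiemetic use.** The primary objective includes "the use of antiemetics among patients with cancer receiving moderate to high emetogenic outpatient chemotherapy regimens" and section 11 treats antiemetic use as primary, but Study Endpoints lists "Outcome Measure Title: Reduction in Antiemetic Use" as the secondary outcome.
- **Visits.** Study Endpoints gives MAT and diary collection at visits 1 to 4. Table 2 and section 11 have three collections, at Visits 1, 2 and 3.

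**The concern.** The endpoint definition and the primary analysis describe different quantities: how bad CINV was, and whether it happened. A logistic model for occurrence does not estimate a difference in mean score.

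The difference matters for this intervention. Under section 9, arm 2 is told to use the inhaler at the first sign of symptoms and as needed after that. If it eases nausea that has already begun, that phase is still recorded as a yes. A benefit of the kind hypothesis 1(a) describes could therefore leave the planned nausea outcomes unchanged.

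Two readings of the primary outcome would also be open once data are in hand. Choosing between them at that stage would expose the result to a charge of selective reporting.

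**Working it through.** The question is whether any planned analysis compares a MAT score between arms. The documents state no figure for this point that could be reproduced, so the check is mainly a comparison of texts.

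**Step 1: what each section specifies for CINV.**

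| Place | Quantity | Type or method |
|---|---|---|
| Study Endpoints, Primary Outcome | Severity | Mean MAT score |
| Section 3, hypothesis 1(a) | Discomfort | Not stated |
| Section 11, General Approach, opening sentence | CINV | Parametric analysis, 3 time points |
| Section 11, General Approach, method sentence | CINV | Binary, logistic regression |
| Section 11, outcome table | CINV by MAT | Binary |
| Section 11, Analysis of the Primary Endpoint(s) | Risk of nausea or vomiting | Logistic regression |
| Section 11, Mixed ANOVA list | Four other outcomes | CINV absent |

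**Step 2: could another sentence supply the missing test?**

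- *The parametric-analysis sentence.* It covers all endpoints in general terms. The method sentence that follows, the outcome table and the primary-endpoint section are more specific, and all three make CINV binary. The specific text governs.
- *The paired t-test and Wilcoxon sentence in section 11.* It concerns pre- and post-assessments, so it is a within-person comparison. Table 2 shows no MAT at the initial visit, so there is no pre value for a MAT score.

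Neither gives a between-arm comparison of a score, and no other passage available for review does.

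**Step 3: is the logistic analysis itself fixed?** Two things are left open. The wording about any of the listed outcomes could mean one composite (any of the four events) or four separate models. The text also does not say how three visits per participant enter the regression.

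**Step 4: error rate under the four-model reading only.** Section 11 sets .05 for all analyses and states no multiplicity adjustment.

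- If the tests are independent: 1 − (1 − 0.05)^4 = 1 − 0.95^4 = 1 − 0.8145 = 0.1855, about 18.5%.
- If the four two-sided test statistics share a common positive correlation (assumed, since the documents give none): about 17% at 0.3 and about 13% at 0.7.

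Under the composite reading there is one test, and this inflation does not arise.

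**The case against.** The strongest reply is that the mean-score phrase is template wording. Study Endpoints also refers to a mean score for the antiemetic diary, which section 9 describes as dates, times and drug names. On that view the binary analysis is what was intended, and only the endpoint description is loose. This is plausible, and it is why counting how many outcomes carry that phrase adds little. It does not explain severity in the outcome title or discomfort in the hypothesis, and it would still leave the primary outcome wrongly described and in need of amendment.

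A second reply is that the MAT, as described, has no intensity item and no scoring rule, so occurrence may be the sounder endpoint. That stands. It means a newly devised score should not be presumed the better repair.

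A reader might also infer stronger things that the documents do not support:

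- *That the binary analysis costs power.* The sample size of 100 comes with no effect size, standard deviation, event rate or power. Which analysis has more power depends on whether the inhaler relieves episodes or prevents them, and on how common symptoms are in the control arm. The documents settle neither.
- *That antiemetic use is the only between-arm measure that could show relief.* Relief in the acute phase could also appear in delayed-phase symptoms, and FACIT-G, which includes physical well-being, is compared between arms. All of these are indirect.
- *That the occurrence outcomes cannot show benefit.* Vomiting and later episodes could still be prevented.
- *That four separate tests are planned.* The wording allows a single composite.
- *That there is a fourth MAT collection.* Table 2 numbers its timepoints 1 to 4, with the MAT collected at the last three, so the visit mismatch may be only labelling.

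**Conclusion.** The contradiction is real and must be fixed. The protocol names severity by mean MAT score as its primary outcome, and the analysis plan provides no between-arm test of it. The section 11 plan for CINV is also incomplete, because it fixes neither the number of tests nor the handling of repeated visits.

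The size is structural: zero planned between-arm analyses of the stated primary outcome. The 18.5% figure is conditional on four separate tests that are independent, and is lower with positive correlation. The conclusion needs no assumption about effect size or symptom rates. It rests on reading the specific sentences of section 11 as governing its general opening one, and on the text available for review.

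**What to change.** Make Study Endpoints and section 11 agree, in a dated amendment made before any outcome data are viewed by arm. If that can no longer be shown, label the resulting analysis post hoc. Staff collect arm-specific packets and all team members can open the analysis file, so the amendment should record who has seen outcomes by arm.

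Two routes are of equal standing:

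- **(a) Occurrence.** Restate the primary outcome as one named endpoint, either a single event or a defined composite. Test it with one logistic model that accounts for repeated visits (GEE or mixed). Treat the other occurrences as supportive, and claim no effect on severity or discomfort.
- **(b) Score.** If a defensible MAT score can be pre-specified from the occurrence, duration and frequency items, state its coding, its value when there are no symptoms, how the acute and delayed phases combine, and the handling of missing items. Compare it between arms over Visits 1 to 3 with one repeated-measures contrast, using the Mixed ANOVA already planned or a linear mixed model. Keep the yes/no outcomes as supportive. The drawback is that, with no scoring rule or intensity item in the protocol, the score must be justified as a measure of severity.

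In either case, reconcile the rank of antiemetic use. If it stays primary, state how .05 is shared or in what order the tests are made. Align the Study Endpoints visit labels with the three MAT and diary collections in Table 2.

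Cost: no new patients, visits or forms. Route (a) is mostly wording plus a repeated-visit model. Route (b) adds the work of devising and justifying a score.
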